For the analysis of the time-normalized number of moderate and/or severe HAE attacks, an analogue calculation will be done using all HAE attacks classified as moderate or severe.

The SGART will be presented descriptively. Comparison of the distribution of responses to therapy between CSL312 and placebo at the end of Treatment Period (Day 182) will be done.

To test for a difference in SGART between CSL312 and placebo, a comparison of the distribution of responses at the end of Treatment Period (Day 182) will be performed by using a two-sided Wilcoxon Test (alpha= 5%).

In addition, the secondary endpoints described above (except the SGART) will be summarized for the first 3 months (Day 1 to Day 91), as well as the second 3 months of the Active and Placebo Arms. Further, the following endpoints will be compared between the Active Arm and the Placebo Arm using the first 3 months (Day 1 to Day 91), as well as the second 3 months (Day 92 to Day 182) in an exploratory manner using the same tests as for the respective main analyses:

- Time-normalized number of HAE attacks per month.
- Percentage reduction in the time-normalized number of HAE attacks.
- Percentage of subjects with a percentage reduction of 100%.
- HAE attacks per month requiring on-demand treatment.

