4.4 Randomization Procedures and Blinding

Subjects will be randomized using a block randomization by means of centralized Interactive Response Technology (IRT) to 1 of 2 treatment arms in a 3:2 ratio to either the Active Arm or to the Placebo Arm. Stratifying variables will be age (\leq 17 years, $>$ 17 years) and, for adults, the subject's baseline attack rate (1 to $<$ 3 attacks/month, and \geq 3 attacks/month).

Randomization will be done centrally. The randomization list will be generated according to the approved randomization specifications, which includes further randomization details. The IRT service provider will keep the randomization code on file. Investigational site staff, including the investigators, will be blinded to treatment allocation. Subjects and CSL staff / designates participating in the conduct of the study will also be blinded to treatment allocation (double-blind).

The IRT will assign the investigational product (IP) to each subject. The IP will be packaged and labelled to ensure blinding is maintained and CSL312 Prefilled Syringe is not distinguishable from the placebo.

Study unblinding will take place following locking of the study database except in the situations as breaking the blind for an emergency or an ad-hoc safety unblinding. Outputs including unblinded information might also be generated for meetings with the independent data monitoring committee (IDMC, see [Section 4.6.3](#)). Adequate procedures are in place to ensure the integrity of the blinded data within CSL.

All blood samples collected for PK / PD analyzed by the central laboratory will remain

blinded until database lock. In addition, results from assessment of aPTT will not be available to subjects, study site personnel, or CSL and their delegates who are blinded to treatment assignment.

The bioanalyst and pharmacokineticist responsible for the sample analysis and PK / PD, immunogenicity, and coagulation evaluations will be unblinded. However, they will agree not to disclose the randomization schedule or any data prior final data base lock and unblinding.

For further details please see the CSP.

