$$[\text{the number of HAE attacks} / \text{length of subject treatment in days}] * 365.25.$$

The time-normalized number of HAE attacks will not be calculated if the subject's observation time for the Treatment Period is less than 30 days, i.e. subject discontinued within 30 days after first study drug administration.

The randomization is stratified by the variables age (≤ 17 years, > 17 years) and, for adults, the subject's baseline attack rate (1 to < 3 attacks/month, and ≥ 3 attacks/month) during the Run-in period. Age and baseline attack rate are not regarded as confounder or effect modifier. The stratification by age is implemented to mitigate the risk that adolescent subjects could be randomized all to the same treatment, with worst case scenario that all adolescents are on placebo treatment. There is no significant physiological basis to suggest different efficacy or safety profiles in adults and adolescents and the distribution of attack locations in adolescent subjects typically mirrors that of adults [[MacGinnitie, 2014](#)].

It is expected that around 50% of subjects will have 1 to < 3 attacks/month and around 50% of subjects will have ≥ 3 attacks/month as baseline attack rate [[Banerji, 2018](#)]. Because of the stratified randomization these two subgroups of subjects will be equally distributed to the Active and to the Placebo arm. It is assumed that the treatment effect, i.e. the time-normalized number of HAE attacks observed under CSL312 treatment, is not impacted by the baseline attack rate. Nevertheless, the time-normalized number of HAE attacks will be compared for

the 6 months of the Active Arm and the 6 months of Placebo Arm using a Poisson Regression model including baseline attack rate as fixed effect in a sensitivity analysis, see [Section 10.1.2](#).

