10.1.2 Primary Efficacy Analysis

Following the estimand described in [Section 10.1.1](#), the primary efficacy endpoint between CSL312 and placebo is tested for a difference by comparing the time-normalized number of HAE attacks in the 6 months of the Active Arm and in the 6-month Placebo Arm period by using a two-sided Wilcoxon Test (Hierarchical Testing H01). The monthly CSL312 dose will be evaluated against monthly placebo at alpha = 5%:

$$H_{01}: a_1 = 0 \text{ versus } H_{11}: a_1 \neq 0$$

In the above hypothesis, the term “ a_1 ” is the shift between the 2 distributions of monthly CSL312 and monthly placebo.

The time-normalized number of HAE attacks per month and per year will be summarized descriptively for the 6 months of the Active Arm and the 6-month Placebo Arm period by median and mean with corresponding 95% CIs.

Sensitivity Analysis considering baseline attack rate

As a sensitivity analysis, the time-normalized number of HAE attacks will be compared for the 6 months of the Active Arm and the 6 months of the Placebo Arm using a generalized linear model (GLM) for count data assuming a Poisson distribution with the logarithm as link function and Pearson chi-square scaling of standard errors to account for potential over dispersion. The model includes treatment (categorical) and the time-normalized baseline attack rate during Run-in Period (continuous) as covariates. To account for the length of subject treatment, the logarithm of the length of subject treatment is used as an offset variable in the model:

$$\log \lambda_i = \log(t_i) + \beta' x_i$$

where λ_i is the expected number of HAE attacks of subject i ($i = 1, \dots, n$ with n the number of subjects in ITT Analysis Set), $\log(t_i)$ is the offset with t_i as the length of the i -th subject treatment in days and x_i is the covariate of subject i which includes the time-normalized baseline attack rate of subject i and the treatment information of subject i .

From this model, the least squares mean time-normalized number of HAE attacks and the standard errors are estimated for CSL312 and placebo. The mean time-normalized number of HAE attacks ratio for CSL312 relative to the placebo and the corresponding 95% confidence interval are also estimated. To report as mean attack rate per month, the received estimates are transformed by the exponential function and scaled by time.

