The mean time-normalized number of HAE attacks ratio for CSL312 relative to placebo and the corresponding 95% confidence interval estimated by the model described above will be used to calculate the percentage difference in the mean time-normalized number of HAE attacks for CSL312 from placebo as:

$$100\% * (\text{mean time-normalized number of HAE attacks ratio} - 1).$$

The 95% CI for the percentage difference will be calculated with the estimated upper and lower confidence limits for the mean time-normalized number of HAE attacks ratio, transform by subtracting 1 and multiplying by 100%.

The sensitivity analysis considering baseline attack rate will be carried out using the ITT Analysis Set.

Technical Note: the time-normalized baseline attack rate during Run-in Period (continuous) will be derived as defined in [Section 10.3.2.1](#).

Sensitivity Analysis for missing values

Missing values occur if the observation time for the treatment period is less than 30 days, i.e., a subject discontinued within 30 days after first study drug administration. Therefore, only a very low number of subjects with a missing primary endpoint are to be expected.

To assess the impact of missing data for the primary efficacy estimand a systematic approach will be applied. For each treatment arm, a range of values for the number of time-normalized HAE attacks per month from 0 to 6 subdivided into 9 increments between two consecutive integer values will be generated. All possible combinations from the subdivided ranges will be imputed to replace the missing values. For the comparison of active treatment versus placebo, observed and imputed data will be analyzed using the Wilcoxon Test and results will be classified into negative (i.e., placebo significantly better), neutral (i.e., no significant difference) and positive (i.e., active treatment significantly better).

A graph where the x-axis presents the subdivided range for placebo and the y-axis the subdivided range for the active treatment will visualize all scenarios and distinguished the different outcomes by different colors and symbols. The total number of subjects with missing outcome in placebo and active treatment arm will be added to the graph. This sensitivity analysis will only be applied to the ITT Analysis Set.

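### H01 is an unadjusted Wilcoxon test although adults are stratified by Run-in attack rate; a rank-ANCOVA on that rate would be a minor efficiency gain, essentially nil at the planned effect

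*SAP*

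**What the plan says.** SAP 4.4 describes the stratification: "Stratifying variables will be age" and, for adults, the Run-in attack rate cut at 3 per month. SAP 10.1.2 then compares the arms "by using a two-sided Wilcoxon Test (Hierarchical Testing H01"), with no stratum or covariate. Protocol 10.3.2.3 names the same test.

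SAP 10.1 gives its reasons:

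- Confounding and effect modification are set aside: "Age and baseline attack rate are not regarded as confounder or effect modifier".
- Stratified randomisation is expected to balance the two baseline-rate groups.
- The treatment effect is assumed stable, "i.e. the time-normalized number of HAE attacks observed under CSL312 treatment, is not impacted by the baseline attack rate".
- The age stratum has a practical purpose: "The stratification by age is implemented to mitigate the risk that adolescent subjects could be randomized all to the same treatment".

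The SAP then adds a Poisson sensitivity model with the continuous Run-in rate. This is the only analysis of the primary endpoint that uses that rate, and it lies outside the test hierarchy in SAP 10.5.

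**The concern.** Adjusting for a baseline variable in a randomised trial is mainly a question of precision. What matters is whether the variable predicts the outcome, and in particular whether subjects with many Run-in attacks go on to have many attacks on placebo. SAP 10.1 does not ask this. Its statement about the CSL312 arm concerns prognosis in that arm only.

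Taken together, the premises would imply more than the SAP says. If the CSL312 rate does not depend on baseline and baseline does not modify the effect, the placebo rate cannot depend on baseline either. The SAP neither states nor supports this. It also sits awkwardly with a design that stratifies on the Run-in rate and uses it as the denominator of a secondary endpoint (SAP 10.3.2.1).

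What is at stake is efficiency. When randomisation balances a prognostic factor and the test ignores it, the test's variance is too large, so it rejects too rarely under the null and loses some power.

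The point is limited to the Run-in rate. The age stratum has a non-prognostic reason, and only about 5 adolescents are targeted (SAP 4.5).

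**Working it through.** **1. The plan's own figure.** Inputs from SAP 4.5: Poisson means 0.3125 and 1.3, 24 against 16 subjects, two-sided 5%.

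- p = P(CSL312 count < placebo count) + ½ P(tie) = 0.767, so the log odds are ln(0.7673 / 0.2327) = 1.193.
- Null term: σ0 = (2/√3) √(T / (0.6 × 0.4)), with T = 1 − Σ m³ over the pooled probabilities m. T = 0.812, so σ0 = 2.124.
- Alternative term from the same two distributions: σ1 = 2.553.
- Power = Φ[(√40 × 1.193 − 1.96 × 2.124) / 2.553] = Φ[(7.546 − 4.163) / 2.553] = Φ(1.325) = 90.7%. Simulation gives 91.7%.
- The next lower exact 3:2 split, 21:14, gives 87.2%.

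The stated 90% therefore reproduces. The model behind it is one month of counts with no between-subject variation, so it cannot show any gain from adjustment.

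**2. The two tests.** Rank the endpoint (R) and the Run-in rate (Q) over both arms, using mid-ranks, and centre both. With b = ΣQR / ΣQ² and residuals e = R − bQ, the statistic is z = Σ(active) e / √[(n1 n2 / N) × Σe² / (N − 1)]. With b = 0 this is the tie-corrected Wilcoxon test without continuity correction.

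**3. Simulation, 6-month endpoint, N = 60.** Placebo mean 1.3 per month, 3:2 blocks stratified on observed Run-in rate, at least 2 Run-in attacks required. Between-subject variation is assumed, because the documents give no Run-in/on-study correlation. Entries are plain Wilcoxon / rank-ANCOVA rejection rates in %; the effect is proportional to baseline.

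Set A: half the latent rates uniform on 1 to 3 per month, half 3 plus an exponential with mean 1.5; gamma frailty with variance 0.1 to 1.0; 20,000 null and 10,000 power trials. ρ is the placebo-arm rank correlation.

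| ρ | null | ratio 0.7 | ratio 0.5 |
|---|---|---|---|
| 0 | 4.9 / 5.1 | 45.3 / 45.5 | 92.8 / 92.7 |
| about 0.20 | 4.6 / 4.9 | 40.8 / 42.4 | 90.2 / 90.9 |
| 0.22 | 4.6 / 5.0 | 16.3 / 17.3 | 44.9 / 47.0 |
| about 0.35 | 4.4 / 5.1 | 30.2 / 34.1 | 80.1 / 83.7 |
| 0.42 | 3.8 / 5.0 | 43.0 / 50.4 | 92.8 / 95.5 |

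Set B: gamma subject rates with the stated coefficient of variation (CV); ρ about 0.3 to 0.6 for CV 0.4 to 0.8; 20,000 trials.

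| CV | null | ratio 0.7 | ratio 0.5 |
|---|---|---|---|
| 0.4 | 4.3 / 5.0 | 68.3 / 69.8 | 99.4 / 99.5 |
| 0.6 | 3.5 / 5.2 | 52.9 / 58.7 | 96.5 / 97.8 |
| 0.8 | 2.7 / 5.1 | 41.9 / 51.9 | 91.9 / 95.7 |

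The largest gain is 50.4 − 43.0 = 7.4 points in Set A and 51.9 − 41.9 = 10.0 in Set B. A third set of assumed variation gave 5 to 17 points at ratio 0.7, with the plain test at 3.2 to 4.3% under the null.

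**4. CSL312 rate independent of baseline**, as SAP 10.1 assumes. The gain at ratio 0.5 to 0.7 is 0.1 to 1.1 points in Set A, and about 0 to 2 points overall.

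**5. Planned effect.** The ratio is 0.3125 / 1.3 = 0.24.

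- Set B: 100.0% for both tests at N = 60, and a difference of at most 0.1 points at N = 40.
- Set A: at least 99.9% for both at N = 60 with frailty variance up to 0.3. At variance 1.0 with a proportional effect, 95.1 / 95.4 at N = 60 and 83.5 / 84.6 at N = 40.

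**6. The SAP's one-month model, ratio 0.24.** At N = 40: 91.9 / 91.8 (CV 0), 89.7 / 89.3 (CV 0.4) and 84.7 / 84.8 (CV 0.8). At N = 60, CV 0.8: 94.8 / 95.3. The change is −0.4 to +0.5 points. At weaker effects with a weakly prognostic baseline the loss approaches 1 point (N = 40, CV 0.4, ratio 0.5: 45.5 / 44.6).

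**The case against.** The strongest reply is that nothing here is broken. The test is valid, the SAP explains its choice, and the Poisson model already supplies a baseline-adjusted comparison. SAP 10.3.2.1 also tests each subject's percentage reduction from Run-in, which is a baseline-relative comparison of the same attacks. The gain needs an effect far weaker than the documents expect: SAP 4.5 plans a ratio of 0.24, and Protocol 3.3.2 predicts a reduction of about 91%. It also largely needs the CSL312 rate to scale with baseline, which SAP 10.1 assumes it does not. Changing the test departs from the one that was powered and would put an adjusted p-value beside unadjusted medians.

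Most of this stands, and it is why the point is minor. The change is not entirely free, since a weakly prognostic Run-in rate could cost up to about 1 point. The sizes depend heavily on assumptions: Set A, for example, has a mean latent Run-in rate of about 3.4 per month but a placebo rate of 1.3, a drop of about 60%. What does not stand is that the other analyses remove the point. The Poisson model is outside the hierarchy, and percentage reduction is a different variable. The mismatch of p-value and estimate can be handled in the reporting.

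A reader might go further and infer that ignoring the stratification inflates type I error or leaves the trial underpowered. The documents do not support either reading. The error runs in the conservative direction, and at the planned effect the choice of test makes almost no difference.

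**Conclusion.** The point holds as a minor efficiency matter. H01 ignores a stratifying baseline rate, and the SAP's reasons do not address its prognostic value on placebo. If the Run-in rate is prognostic, the plain test rejects about 3 to 4.5% of the time under the null instead of 5%. At ratios of 0.5 to 0.7 it gives up roughly 1 to 10 points of power or more with a proportional effect, and about 0 to 2 points if the CSL312 rate is independent of baseline. At the planned ratio the loss on the 6-month endpoint is essentially nil, reaching about 1 point only at N = 40 under the largest variation in Set A. All of this depends on an assumed correlation, and none of the ranges is a bound.

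A separate minor item adds no weight to the above. Protocol 10.3.2.3 has age as a covariate in the Poisson model and SAP 10.1.2 does not, yet SAP 5 declares no further changes. That discrepancy needs no assumptions.

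**What to change.** Test H01 with one named test: the rank-ANCOVA (Quade form) set out above, on the continuous Run-in rate already derived in SAP 10.3.2.1, two-sided 5%. Keep the plain Wilcoxon test as a sensitivity analysis. State a rule for a subject randomised in error without a Run-in rate, for example the mean rank.

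Carry the same test through:

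- the per-protocol analysis of the endpoint;
- the missing-data grid in SAP 10.1.2, where at present "observed and imputed data will be analyzed using the Wilcoxon Test";
- the 3-month comparisons in SAP 10.3.2.4, because Protocol 10.3.2.4 requires these "using the same tests as for the respective main analyses";
- for consistency, the attack rates requiring on-demand treatment and the moderate or severe attack rates (SAP 10.3.2.2 and 10.3.2.3).

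Reword the H01 parameter, which now "is the shift between the 2 distributions of monthly CSL312 and monthly placebo": under H01 the distribution of the endpoint given the Run-in rate is the same in both arms. Keep the unadjusted medians and means as descriptive estimates, and report the adjusted rate ratio from the existing Poisson model beside them. List the change of test in SAP 5. Separately, restore age to the Poisson model or declare its removal there.

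The cost is text in several SAP sections. No new data are needed, because Protocol 4.1.3 requires a Run-in period with attacks, so every eligible randomised subject has the rate. The sample size can stay, since power at the planned effect is not materially lower.

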10.1.1 Primary Estimand

The primary interest is to assess the treatment effect of CSL312 during treatment from Day 1 through Day 182 while subjects are allowed to treat HAE attacks with on-demand medications.

The primary estimand in line with the primary interest of the study follows the treatment policy strategy and is described as follows:

- Treatment Condition: monthly treatment of CSL312 or placebo
- Population: the target patient population defined by eligibility criteria and who were randomized (ITT).
- Variable: time-normalized number of HAE attacks per month during treatment from Day 1 through Day 182.

Intercurrent events: The occurrence of an intercurrent event is irrelevant. All observed values will be used regardless of occurrence of any of the following intercurrent events:

- administration of on-demand medication in addition to prophylactic treatment with CSL312,
- Prohibited concomitant medications due or not due to COVID-19 or COVID-19 vaccination,
- non-compliance to treatment due or not due to COVID-19 or COVID-19 vaccination,
- early study discontinuation due or not due to COVID-19.

- Population-level summary: median time-normalized number of HAE attacks per month during treatment from Day 1 through Day 182 by treatment.

If a subject discontinued the study early after being continuously the first 30 days in the treatment period, the observation is terminated by the Early Termination Visit. It is assumed that the attack rate for subjects, who discontinued the study after the 30th study day and before the end of the 6th month, is comparable to the attack rate from subjects who have the entire 6 months treatment period observed. This assumption is based on CSL312_2001 data which showed that the CSL312 treatment effect was maintained over time. Therefore, the primary endpoint will be considered measurable and not missing, ie, the time-normalized number of HAE attacks will be calculated based on the HAE attacks reported until the Early Termination Visit.

In case a subject discontinues study treatment due or not due to COVID-19 but continues participation in the study for more than 30 days beyond the last study drug administration,

the HAE attacks until the last study drug administration plus 30 days will be included in the HAE attack analysis and length of subject treatment in days will be derived as:

[date of last study drug administration – the date of Study Visit Day 1 of the Treatment Period +31].

Missing data is only given if subjects discontinue the study within 30 days after the first study drug administration in the treatment period. An approach to handle these missing data by sensitivity analysis is described in Section 10.1.2.

During the BDRM, it will be assessed if subjects have missed subsequent study drug administrations and if this might lead to the exclusion of subject's data from the analyses. All decisions will be documented in the BDRM minutes.

A COVID-19 diagnosis and resulting intercurrent events are irrelevant for the primary estimand. All observed values will be used regardless of occurrence of any of the following COVID-19 related intercurrent events: medications given to treat COVID-19 or COVID-19 vaccinations. Non-compliance to treatment and early discontinuation will be handled the same independent if it is related to COVID-19 or not.

